- b. **Secondary outcomes** are glucose iAUC obtained during the oral glucose tolerance test; mean iAUC as obtained from 24hr- continuous glucose monitoring, and Mean Amplitude Glycemic Excursion (MAGE) as obtained from 24hr- continuous glucose monitoring. Tertiary outcomes are cognitive function (working memory, inhibition, attention, and processing speed), mood, anxiety, daily physical activity (steps counts/day), and dietary intake at the final test meal. Improved circulating glucose values as demonstrated by lower glucose iAUC would directly support our primary insulin outcome and would be clinically relevant as this result would indicate improved metabolism. Additionally, MAGE has been demonstrated to be associated with metabolic control such that elevated MAGE is associated with worsening cardiometabolic outcomes in individuals with diabetes.¹⁶⁷

The executive function, mood and anxiety outcomes are being collected for independent objectives. This group of measures is an important objective to provide information that will be necessary to know for feasibility of this intervention. This intervention is poised to community application such as school class rooms. Therefore, it is important to understand if executive function is adversely affected by the intervention as this would limit its feasibility for implementation. Finally, all analyses will be performed within the subgroups of healthy weight and overweight subjects to evaluate for differential effectiveness based on weight status.

10. Statistical Analysis

- a. Analysis of data.** Prior to conducting the main model analysis, descriptive analyses will be conducted on all outcome and covariate to assess potential outliers and calculate summary statistics. If significant deviations from the assumed distribution (e.g.: normal) occur, then appropriate transformations will be applied to fulfill model assumptions. If transformations are not sufficient to meet model assumptions, then nonparametric tests will be used. Descriptive statistics will investigate correlations between variables at pre-test and post-test to assess potential confounders prior to analyses.

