The parallel study design allows for the examination of between-individual comparisons of test effects and within-individual longitudinal test effects (i.e. repeated daily CGM metrics). Significance level will be set at $\alpha = 0.05$. Covariates will include: age, sex, race/ethnicity, baseline cognitive ability (for cognitive outcomes only), baseline homeostatic model of insulin resistance (HOMA-IR), body fat mass (except for subgroup analysis by weight status), and Tanner stage. We will also evaluate for a weight status interaction (intervention x healthy weight / overweight).

The following analyses will be performed:

- i.** Participant characteristics will be summarized using means (standard deviations) and frequencies.
- ii.** Baseline (time 0) values for participant characteristics, insulin, glucose, heart rate, and blood pressure between the groups will be compared using t-tests.
- iii.** The primary analysis will be ANCOVA comparing children randomized to the two groups for insulin iAUC at the end-study oral glucose tolerance test, with age, sex, race/ethnicity, HOMA-IR, body fat mass, and Tanner stage as variables in the model. If all covariates are nonsignificant, unpaired t-tests will be reported for the differences in OGTT insulin iAUC by condition (prolonged vs interrupted sitting). Similar analyses will be used to examine glucose iAUC, 5- or 6-day average 24hr CGM iAUC and 24hr MAGE. (Subjects may only have 5 days of CGM data if a device is

accidentally removed and replaced at the next visit or subject uses a medication that interacts with glucose readings such as acetaminophen-after which 24hrs of data will be omitted from analysis). Mixed models will also be used to assess the influence of prolonged vs. interrupted sitting on insulin and glucose iAUC over the 3 hours of observation. To evaluate differences in the dependent variables at each time point, planned comparisons of model-based mean differences between each time points will be calculated. Additionally, mixed models will be used to assess condition influence on mean 24hr CGM glucose iAUC and 24hr MAGE.

- iv. ANCOVA or (as indicated above) t-tests will investigate differences in working memory, inhibition, attention, processing speed, mood, anxiety, and kcal intake between prolonged sitting and interrupted sitting at the post- test.

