- v. Mixed models will also be used to assess the influence of prolonged vs. interrupted sitting on change in cognitive function, mood and anxiety (pre-post test scores) controlled for significant covariates. Covariates to be considered include those listed above in addition to free living activity and sleep.
- vi. As a secondary analysis, all the analyses described above will be performed on the subgroups: Healthy weight and overweight subjects.
- vii. Supplemental MRS Study: Repeated measures ANOVA will investigate the change in IMCL content between baseline & pre-session (thus, evaluating for daily intervention effect) as well as immediately pre- and post-intervention session (thus, evaluating the immediate effect of intervention) by condition. ANCOVA analyses will compare the change in IMCL content by condition with age, sex, race/ethnicity, HOMA-IR, body fat mass, and Tanner stage as variables in the model.

b. Power Analysis

Based on our preliminary published data,⁶⁵ and our unpublished data in overweight youth, we expect a moderate to large (Cohen's $d = 0.8$) effect size. With an 80% power, $\alpha=0.05$, our sample size requires evaluable data from 21 in each group; with our goal of subgroup analysis within healthy weight and overweight groups, we will require 84 participants total (42 overweight and 42 healthy weight). This is supported by previously reported adult data published by Dunstan et al. who identified the mean (standard

deviation) difference between the two groups was 191.0 (334.9) pmol/L yielding a moderate to large effect size.⁴⁸ Taking into consideration more variability due to the parallel design (versus cross over designs used previously), we will randomize up to 120 participants and estimate that at most 36 children will drop-out of the study before completion. We expect at least 84 participants to complete the protocol which is our target completion based on these analyses.

11. Human Participant Protections

a. Rationale for subject selection

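### Differential effectiveness by weight status is assigned to separate subgroup analyses, and the planned interaction test is not made the basis for claiming a difference

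*Combined protocol and SAP*

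**What the plan says.** Three places bear on this point.

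- Section 9.b, at the end of the secondary outcomes: "all analyses will be performed within the subgroups of healthy weight and overweight subjects to evaluate for differential effectiveness based on weight status". Item vi of Section 10.a repeats this as a secondary analysis and gives no rule for comparing the two sets of results.
- Section 10.a, in the paragraph before the numbered analyses: "We will also evaluate for a weight status interaction (intervention x healthy weight / overweight". The interaction does not reappear in items i to vii. No purpose, power or precision is given for it.
- Section 10.b, on sample size: "with our goal of subgroup analysis within healthy weight and overweight groups, we will require 84 participants total".

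The plan does not say which result governs if the subgroup analyses and the interaction point in different directions. Section 10.a also leaves body fat mass out of the subgroup models, so these are not the whole-sample model restricted to each group.

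**The concern.** Whether an effect differs between two groups is a question about the difference between two estimates. Two separate tests against zero do not answer it. Two groups with the same true effect will often fall on opposite sides of 0.05 by chance, and two groups with different effects can both be significant. Section 9.b nevertheless names the within-group analyses as the means of judging differential effectiveness.

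The equal-effect case is the one the protocol expects. The Subject Selection text in Section 1 anticipates equal effects in healthy weight and overweight children, and Section 11.a cites pilot data suggesting similar insulin effects. The protocol's own background shows how a split can arise: in the preliminary data, glucose iAUC differed at P = .018 in 28 healthy weight children but not in 37 overweight children (p = 0.12), and no between-cohort comparison is given. Glucose iAUC is a secondary outcome of this trial.

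At stake is a report that interrupting sitting works in only one weight group when the effects are equal. The protocol wants evidence of benefit in all the populations where a community programme would be used, so that report would misdirect the next step.

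**Working it through.** **Inputs**

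- Effect size, Section 10.b: "we expect a moderate to large (Cohen's $d = 0.8$) effect size".
- Power and evaluable number, Section 10.b: "With an 80% power, $\alpha=0.05$, our sample size requires evaluable data from 21 in each group".
- Total, Section 10.b: "we will require 84 participants total (42 overweight and 42 healthy weight". With two arms this is 21 per arm in each weight group.
- Attrition, Section 10.b: "we will randomize up to 120 participants and estimate that at most 36 children will drop-out of the study before completion". The accrual table gives 60 randomized per weight cohort, so at most 30 per arm in each.
- Assumptions: 1:1 allocation (the ratio is not stated in figures), unadjusted t-tests, SD = 1. Sidedness is not stated; two-sided 5% is used unless noted.

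**Step 1: the plan's own figure.** For two means, n per arm = 2(z_alpha + z_power)² / d².

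- One-sided 5%: 2(1.645 + 0.842)² / 0.64 = 19.3. The noncentral t gives 20.03, rounded up to 21. Power at 21 is 81.7%.
- Two-sided 5%: 2(1.960 + 0.842)² / 0.64 = 24.5. The noncentral t gives 25.5, rounded up to 26. Power at 21 is 71.6%.

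So 21 reproduces only with a one-sided test. Then 21 × 2 arms × 2 weight groups = 84, and 120 − 36 = 84.

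**Step 2: discordant subgroup results when the true effect is equal.** The two weight groups contain different children, so the tests are independent. With power p in each, the chance that exactly one is significant is 2p(1 − p).

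| Scenario | p | 2p(1 − p) |
|---|---|---|
| Stated 80% power | 0.800 | 32% |
| d = 0.8, 21 per arm, one-sided | 0.817 | 30% |
| d = 0.4, 21 per arm | 0.244 | 37% |
| d = 0.5, 21 per arm | 0.353 | 46% |
| d = 0.6, 21 per arm | 0.475 | 50% |
| d = 0.7, 21 per arm | 0.600 | 48% |
| d = 0.8, 21 per arm | 0.716 | 41% |
| d = 0.9, 21 per arm | 0.812 | 31% |
| d = 1.0, 21 per arm | 0.885 | 20% |
| d = 0.8, 30 per arm (all 120 evaluable) | 0.861 | 24% |
| No effect in either group | 0.050 | 9.5% |

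The chance reaches one third only when subgroup power lies between about 21% and 79%.

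**Step 3: the interaction test in the same situation.** In 60,000 simulated trials with d = 0.8 in both groups, the interaction was significant in 4.98% at 21 per cell and 4.96% at 30 per cell. At 21 per cell, 40.8% of trials had discordant subgroups, and 4.4% had discordant subgroups together with a significant interaction. The two analyses would therefore point different ways in 40.8 − 4.4 = 36.4% of trials, which is why it matters which one governs.

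**Step 4: precision of the interaction.** The unadjusted standard error is √(4/n) SD, with n per cell.

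- n = 21: √(4/21) = 0.436, so the 95% half-width is 1.96 × 0.436 = 0.86 SD.
- n = 30: √(4/30) = 0.365, so the half-width is 1.96 × 0.365 = 0.72 SD.
- Power at 21 per cell is about 15% for a 0.4 SD difference in effects and 44 to 45% for 0.8 SD (noncentral t and normal approximation respectively).
- 80% power needs a difference of about 1.24 SD at 21 per cell, or 1.03 SD at 30.

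**The case against.** The strongest reply is that the right test is already in the plan. The interaction is prespecified in the general modelling paragraph of Section 10.a, while item vi labels the subgroup work secondary. The word also follows the covariate list and need not make the interaction subordinate. No section says that a difference will be declared when one group is significant and the other is not; Section 9.b is compatible with comparing subgroup estimates alongside the interaction. Sizing each weight group separately has its own justification, since Section 1 wants benefit shown in every population where the approach would be applied. The study is a pilot, and its whole-sample primary ANCOVA is untouched.

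Much of this stands. A reader might infer that the plan judges differential effectiveness from separate tests alone and would find a false difference in a third or more of trials. The documents do not support that: the interaction is planned, the one-significant-one-not rule is not written anywhere, and the percentage depends on the true effect, the evaluable number, sidedness and covariate adjustment. As an illustration, if covariates explained 30% of the variance (an assumption), d = 0.8 would act like 0.8/√0.7 = 0.96, and the discordance at 21 per arm would be about 25%. The subgroup sizing does not by itself show that subgroup p-values will decide the question.

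What the reply does not remove is that Section 9.b gives the subgroup analyses this job in words, and that no text gives it to the interaction.

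**Conclusion.** The concern holds as a gap in what decides. Differential effectiveness is assigned to within-group analyses, which cannot establish it, and the planned interaction has no stated role in the conclusion. The harm is conditional on the subgroup results being read by significance in one group and not in the other. On that reading, an equal true effect gives discordant results in about 32% of trials at the stated power, and the other scenarios tabulated range from 9.5% (no effect) to 50% (d = 0.6), against about 5% for the interaction. These figures rest on unadjusted tests, 1:1 allocation and, apart from the stated-power and one-sided rows, an assumed two-sided 5% level.

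The opposite error also needs guarding against. The interaction is imprecise at this size, with an unadjusted half-width of roughly 0.7 to 0.9 SD, so a nonsignificant interaction must not be read as proof of equal effects. The whole-sample primary comparison of insulin iAUC is not affected.

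**What to change.** In Sections 9.b and 10.a.vi, state that:

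- any claim of differential effectiveness rests on the already planned intervention-by-weight-status term in the whole-sample model, reported as an estimate with its 95% confidence interval;
- effects within each weight group are presented as estimates with confidence intervals, and no difference is claimed because one is significant and the other is not;
- a nonsignificant interaction is not evidence of equal effects, and the interval shows which differences remain compatible with the data.

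If an expected precision is added, label it as unadjusted and give it as a range (about 0.86 SD at 21 per cell to 0.72 SD at 30). Neither figure should be written in as the precision of the adjusted ANCOVA.

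The cost is wording only. No new data, participants or models are needed.

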- c. Any significant drop in systolic blood pressure or a failure of systolic blood pressure to rise in the presence of increasing workload.
- d. Signs and symptoms indicating potential hazard to the patient such as pain, headache, dizziness, syncope, excessive dyspnea or fatigue.
- e. A > 3 mm ST segment depression or elevation.
- f. Significant arrhythmia precipitated by exercise such as PVC's with increasing frequency, supraventricular tachycardia, ventricular tachycardia or atrioventricular block.
- g. Excessive rise in blood pressure: systolic blood pressure >250 mm Hg.
- h. Failure of the monitoring system.

d. Study procedures

All procedures are for research purposes; there is no provision of standard medical care. Participants found eligible after screening will be scheduled for 6 visits (Days #1-6) on consecutive days. Participants will be randomized to one of the two conditions for all of their subsequent visits. Randomization will be done by randomizing each subject to a single treatment by using the method of randomly permuted blocks with average block size 4. Subjects will be stratified by sex (M, F), age (7-9.49 vs. 9.5-11.99y) weight status (BMI < 85th percentile vs. ≥ 85th percentile), and IPAQ result (low, moderate, and high usual physical activity) to promote similar subject characteristics in the two groups.

See **Appendix B** study visit flow table.

i. Test Days #1-6 Daily Procedures:

- a. **Vital Signs.** Blood pressure, height (in cm), weight (in kg), temperature, respiratory rate, and pulse rate will be obtained.

- b. Questionnaires.** Parents and/or participants will answer a brief health questionnaire about participants' medication use, general health, and sleep duration in the previous 24-hours, see Appendix G. Additionally, a 24hr food recall will be administered.
- c. Randomized condition.** Each participant will execute their assigned randomized condition as follows:
- (i) Sedentary condition.** The participant will execute 3 hours of sedentary (seated or recumbent) activity of their choice. Activity monitoring (described below) will be obtained. Continuous heart rate monitoring (described below) will be obtained on test visit #6.

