- e. **Continuous glucose monitoring:** Beginning on day #1 of testing/intervention, a continuous glucose monitor (Libre Pro, Abbott products) will be placed on each child to record glucose trends continuously throughout their 6-day study. The Libre Pro device will be evaluated for placement, skin irritation, function, and data collection daily at each testing visit. It is expected that only 1 device will need to be placed to complete the entire 6-day study. On Day #6, the final day of testing, the Libre Pro device will be removed. Continuous glucose monitoring data will allow calculation of average daily glucose iAUC as well as mean amplitude glycemic excursion (MAGE; the arithmetic mean of all increases or decreases in glucose that exceed 1 SD of the total set of glucose values). If a device is lost/falls off between study sessions, a replacement device will be placed on the subject. If a child consumes a listed medication known to interact with glucose readings (acetaminophen, vitamin C, and aspirin), the following 24hrs of CGM data will be admitted from their analyses but the device will otherwise remain on the subject to continue collecting data throughout the remainder of their study block.
- f. **Continuous physical activity monitoring:** On day #1 of testing/intervention participants will be given a wrist accelerometer (Actigraph GT3X+) to wear continuously throughout their 6-day intervention to assess in-study as well as free-living activity, sedentary behavior, and sleep efficiency. This device will also be removed on day #6 and data will be downloaded. These data will be used to determine if physical activity outside of the test condition changes as a result of intervention. Additionally, the participant will be fitted with a hip accelerometer on test visit #6, which will be worn for the entirety of test visit #6. These monitors will provide added data to evaluate fidelity of the interventions.

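### Minor: covariate p-values decide whether the primary insulin iAUC result comes from the ANCOVA or a t-test, and item v selects its adjusters the same way, some recorded after randomisation

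*Combined protocol and SAP*

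**What the plan says.** All references are to the combined protocol and SAP.

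- **Section 10.a item iii** makes an ANCOVA the primary analysis of insulin iAUC, "with age, sex, race/ethnicity, HOMA-IR, body fat mass, and Tanner stage as variables in the model". The next sentence is the switch: "If all covariates are nonsignificant, unpaired t-tests will be reported for the differences in OGTT insulin iAUC by condition". Glucose iAUC, CGM iAUC and MAGE are to be analysed similarly.
- **Item iv** reads "ANCOVA or (as indicated above) t-tests will investigate differences in working memory" and continues to the other cognitive outcomes, mood, anxiety and intake. The either/or wording shows that the t-test replaces the ANCOVA and is not an addition to it.
- **Item v** models change in cognition, "mood and anxiety (pre-post test scores) controlled for significant covariates", and adds: "Covariates to be considered include those listed above in addition to free living activity and sleep".
- **Item vi** extends everything to healthy-weight and overweight children: "As a secondary analysis, all the analyses described above will be performed on the subgroups".
- **Item vii** (MRS) uses an ANCOVA with the same six covariates and no switch.
- **Section 4.d** stratifies randomisation by sex, age group, weight status and "IPAQ result (low, moderate, and high usual physical activity) to promote similar subject characteristics in the two groups". Weight status and IPAQ level are not in the item iii model.
- **Section 4.d.i.f** has the wrist accelerometer worn from day 1 to day 6 to record activity and sleep, and says of it: "These data will be used to determine if physical activity outside of the test condition changes as a result of intervention".

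No other section fixes the ANCOVA as the reported result.

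**The concern.** A model chosen by the significance of its covariates is chosen from outcome data. With 84 children, or 42 in a weight group, a nonsignificant covariate has not been shown to be irrelevant. The two candidate models can also fall on opposite sides of 0.05. The rule is not fully defined either: it gives no separate threshold for the covariate tests, and does not say whether race/ethnicity and Tanner stage are judged jointly or level by level.

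Item v raises a further matter. Free-living activity and sleep are measured while the intervention is running, and Objective 2 and section 9.b treat activity as an outcome. If the intervention changes either one, adjusting for it can distort the comparison.

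At stake is whether the model behind the primary result is known before the data are seen.

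**Working it through.** **1. The plan's figures.** Section 10.b gives d = 0.8 and 21 evaluable per group, so 4 x 21 = 84 in total and 42 per weight group. For 21 per arm, the noncentrality is 0.8 x sqrt(21/2) = 2.59 on 40 df. Power is 71.6% two-sided and 81.7% one-sided, so 21 meets the stated 80% only one-sided. Sidedness is not stated and is a separate question; two-sided 0.05 is used below.

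**2. How often the switch fires if no covariate matters.** With six independent tests, 0.95^6 = 0.735. In the weight groups section 10.a drops body fat mass, leaving 0.95^5 = 0.774. Judging categorical covariates level by level adds tests: eight give 0.95^8 = 0.663 and ten give 0.95^10 = 0.599.

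**3. Simulation.** The documents give no covariate effects, so four settings were assumed, with residual SD 1.
- Design: 120 randomised in blocks of 4 within 24 strata; 42 of 60 per weight group analysed.
- Race/ethnicity has 4 levels and Tanner stage 3, each tested jointly. HOMA-IR correlates 0.5 with fat mass.
- Effects (none / weak / moderate / strong): fat mass and HOMA-IR per SD 0 / 0.1 / 0.25 / 0.5; IPAQ per level 0 / 0.05 / 0.15 / 0.3; age per SD, Tanner per level, sex and the largest race contrast each 0 / 0.05 / 0.1 / 0.2.
- 8,000 trials per setting. Monte Carlo SE is about 0.25 points for type I error and at most 0.8 for power.

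| % (power and disagreement at 0.8 SD) | None | Weak | Moderate | Strong |
|---|---|---|---|---|
| Switch fires, pooled | 75.2 | 63.3 | 17.6 | 0.0 |
| Switch fires, weight group | 79.0 | 74.2 | 49.1 | 9.7 |
| Fires and models disagree, pooled | 2.7 | 2.4 | 1.2 | 0.0 |
| Fires and models disagree, weight group | 11.1 | 10.6 | 7.1 | 1.8 |
| Type I error of the rule, pooled | 5.5 | 5.3 | 5.1 | 4.4 |
| Type I error of the rule, weight group | 5.4 | 5.7 | 5.5 | 5.0 |
| Pooled power: current rule | 94.9 | 93.5 | 92.5 | 92.1 |
| Pooled power: listed ANCOVA always | 93.0 | 92.4 | 92.4 | 92.1 |
| Pooled power: plus weight status and IPAQ | 92.5 | 92.0 | 92.2 | 92.5 |
| Weight-group power: current rule | 70.8 | 68.6 | 63.8 | 55.7 |
| Weight-group power: listed ANCOVA always | 62.6 | 61.8 | 60.9 | 55.4 |
| Weight-group power: plus IPAQ | 61.2 | 60.2 | 59.8 | 56.0 |

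Level-by-level instead of joint testing moves the pooled firing rate with no effects from 75.2% to 66.5%. At 0.4 SD, an effect the documents do not give, firing with disagreement reaches 6.6% pooled and 7.9% in a weight group.

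**4. Cross-checks.** A simpler simulation without strata or IPAQ (2,000 trials per cell) gave firing with disagreement of 2.8, 2.4, 1.0 and 0.0% pooled, and 13, 12, 7 and 1% in a weight group. Hence the rounded ranges of 0-3% and 2-13%. Another, with six independent covariates and all prognostic strength in one, gave pooled firing of 75, 38, 15 and 1% at R2 of 0, 0.05, 0.10 and 0.20, and about 0 from 0.30. Type I error of the rule there was 4.7-5.2% at n = 84 and 5.0-5.7% at n = 42.

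**5. Adding the missing randomisation factors.** Weight status and IPAQ change the pooled SE by +1.2, +1.1, +0.5 and -1.8%. IPAQ changes the weight-group SE by +1.7, +1.7, +1.0 and -1.0%.

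**The case against.** The rule is written down in advance and allows only two results: the full list or none. Covariate tests, not the treatment p-value, decide between them. HOMA-IR and fat mass are on the list and the outcome is insulin, so moderate to strong effects are more plausible than none. At that end the switch fires in 0-18% of pooled trials and changes the conclusion in at most 1.2%. The study also calls itself a pilot. Deleting the switch never raises pooled power and costs weight-group power in most settings. Section 10.a already lists covariates, including baseline cognitive ability for cognitive outcomes, and plans a weight-status interaction.

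Most of this stands, and is why the point is minor. Part of the rule's weight-group power advantage goes with its type I error of 5.4-5.7% in the first three settings, but the trade-off is real.

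Stronger readings are tempting and not supported:
- **Inflated type I error or bias from the switch.** The error rates above stay close to 5%.
- **Room to pick the favourable result because the trial is un-blinded.** The rule offers no choice by treatment p-value.
- **Frequent conflict between the models.** With a true effect, the six-independent-covariate simulation has ANCOVA and t-test disagreeing in 8-23% of trials at n = 84 (0.57 SD) and 13-24% at n = 42 (0.8 SD). Those rates count every disagreement, whether or not the switch fires, and do not measure harm from the rule.
- **Bias from leaving out two randomisation factors.** Omission causes none; precision is lost only if the factors are prognostic.

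What the objection does not answer is that the primary model is still settled by outcome data, and that item v can bring in variables recorded after randomisation.

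**Conclusion.** The concern holds as a minor one. The reported primary model depends on the trial's outcome data, and the same habit runs through items iv to vi. In the pooled primary analysis the switch fires and changes the conclusion in about 0-3% of trials at 0.8 SD, and it almost never fires if HOMA-IR or fat mass is strongly prognostic. In the weight groups the figure is about 2-13%. All these figures rest on assumed covariate effects, two-sided testing and 84 analysed children. The gain from a change is one model known in advance, not error control.

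Item v's post-randomisation adjusters are a separate reason to edit that item. The documents do not allow the size of any distortion to be calculated, and the finding of no bias applies to the switch, not to those adjusters.

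**What to change.** - **Item iii:** delete the t-test sentence. Report the pre-specified ANCOVA whatever the covariate p-values, with the unadjusted difference as a labelled sensitivity analysis.
- **Item iv:** do the same, using the covariates already listed in section 10.a, including baseline cognitive ability for cognitive outcomes.
- **Item v:** use that same fixed baseline list and remove free-living activity and sleep as adjusters.
- **Randomisation factors:** add weight status and IPAQ level to the pooled model and IPAQ level to the weight-group models, so that the analysis matches the stratified randomisation. IPAQ is already collected at screening.

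**Cost.** Wording only, with no new data, plus three degrees of freedom pooled and two in each weight group. Relative to the current rule at 0.8 SD (none, weak, moderate, strong effects), power changes as follows:
- Pooled, with both added factors: -2.4, -1.5, -0.3 and +0.4 points.
- Weight groups, deleting the switch alone: about -8, -7, -3 and 0 points.
- Weight groups, adding IPAQ as well: about -10, -8, -4 and 0 points.

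A shorter fixed list for the weight groups (age, sex, HOMA-IR, IPAQ) is an option to consider, not a recommendation. It gave power of 68.4, 66.7, 65.1 and 63.5%, against 71.1, 69.1, 63.9 and 56.1% for the rule on the same trials, but this depends on the small race/ethnicity and Tanner effects assumed.

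**Separate point.** The Précis names both CGM and insulin iAUC as primary measures, while sections 9.a and 9.b make insulin iAUC the sole primary and the CGM measures secondary. These sections must be reconciled.
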